7.4 Eligibility

The inclusion and exclusion criteria will be reviewed. Participants are eligible for participation in the study if all the inclusion criteria are met and none of the exclusion criteria are met. If the participant fails to fulfill any of the eligibility criteria, this will be documented. The PI or designee will sign and date the CRF indicating agreement with the determination of eligibility.

If the participant fails to fulfill any element of the inclusion and exclusion criteria, the participant will be classified as a screen failure and will not be advanced any further into the clinical study.

7.5 Baseline Data

The following demographic information will be obtained and documented on the CRF for all enrolled participants:

Age

Sex

Race

Ethnicity

Height (inches)

Weight (pounds)

Wipe the lateral forehead with an alcohol wipe. Place the 3M SpotOn® zero-heat-flux temperature sensor on the participant's forehead.

Record the patient temperature (°C) using the 3M SpotOn® zero-heat-flux forehead sensor, the Braun ThermoScan 7 tympanic sensor, and an MRI compatible axillary sensor.

Remove the 3M SpotOn® zero-heat-flux forehead sensor and the Braun ThermoScan 7 tympanic sensor before escorting to MRI suite.

7.6 Procedure

7.6.1 **VCool System Set Up**

Attach the disposable delivery tube to the VCool System

Install the gas inlet filter on the back with the filter bowl vertical (glass side down)

Attach the air hose to the gas inlet filter

Connect the power cord to a grounded outlet

Turn the power switch to "ON"

Connect the RS232 cable to the VCool System and to the laptop computer

Turn on the computer

Select the following:

TC-48-20 program.

COM5

Communications

Set Point and set value to -19.0

Controller options

Save data to file

Go to file Explorer, select LabView Data

Select New and enter participant identification number as file name

Save data to file

Turn on gas and set flow meter to 35 liters per minute.

Confirm temperature is set to -10°C

Confirm gas temperature setting at the end of the delivery tube is -5°C

Attach nasal cannula to the delivery tube

7.6.2 *MR Imaging procedure*

- Participants will undergo MRI at the HSF3 research facility at the University of Maryland, Baltimore (UIMB). Each imaging session will last approximately 90 minutes. The protocol will include high-resolution anatomical MRI for structural reference and tissue segmentation; MR Spectroscopy (MRS) to measure metabolite and water resonance frequencies for temperature estimation; MR Thermometry to measure phase changes over time to track temperature dynamics; Perfusion MRI to measure cerebral blood flow (CBF); as well as other structural and functional imaging sequences. These sequences will be repeated at multiple time points during the controlled cooling period to monitor temporal changes in temperature, perfusion, and tissue properties.

7.6.3 *Participant Set Up and Monitoring*

Have the participant lie on their back in an inclined position and place the nasal cannula on the participant, securing the straps around their head

Record the temperature from both temperature sensors and record the time

Record the flow rate

Initiate the cooling and record the time. The induction phase for participant cooling can take up to 2 hours.

Record the core body temperature every 2 minutes from both temperature sensors and record the time. The core body temperature is monitored throughout the study.

If the core body temperature is <35°C for 5 minutes:

1. Remove nasal cannula, if temperature starts to rise after 2 minutes keep cannula off until temperature gets back to 35°C. Then reapply nasal cannula and resume treatment.
2. If temperature continues to fall below 35°C after 2 minutes, cover patient with electric blanket that has been pre heated on standby. Keep blanket on until temperature gets back to 35°C.

Assess for shivering every 10 minutes using the BSAS. Record the results and time. The BSAS is recorded throughout the study.

Bedside Shivering Assessment Scale

0	None
1	Mild: Shivering localized to neck/thorax
2	Moderate: Intermittent involvement of the upper extremities and/or thorax
3	Severe: Generalized shivering or sustained upper and/or lower extremity shivering

The flow can be increased to 40 liters per minute after 10 minutes

Record any VCool System adjustments to flow rate or temperature and record the new flow rate and temperature and time of adjustment. Record the reason for the adjustment.

Assess the participant for adverse events (AEs) throughout the study

If the participant has a nosebleed, discontinue the study and note the time.

Monitor patient at first sign of shivering

- If **Mild**, cover patient with regular blanket.
- If **Moderate or severe** – discontinue cooling treatment.

Continue to record the temperature until either temperature sensor reaches 35.5°C or the VCool System has been used for 2 hours. Note the time the target temperature was achieved.

If the participant's core body temperature does not reach 35.5°C in 2 hours, the study is concluded

- Remove the nasal cannula from the participant and dispose of it properly
- Monitor the participant's core body temperature until it returns to baseline. Blankets can be applied to help with warming.
- Remove the axillary thermometer

If the participant's core body temperature reaches 35.5°C, proceed to the next steps

Maintain the target temperature of 35.0°C to 36.0°C for 1 hour:

Adjust flow rate by 5 liters per minute from baseline every 2 minutes

- If temperature falls below 35°C., reduce flow rate by 5 liters per minute every 2 minutes until temperature rises back to 35°C
- If temperature rises above 36°C, increase flowrate 5 liters per minute every 2 minutes until temp falls below 36°C

Remove the nasal cannula and the air delivery tube and dispose of them properly

Once out of the MRI suite, record the patient temperature (°C) using the 3M SpotOn® zero-heat-flux forehead sensor, the Braun ThermoScan 7 tympanic sensor

Monitor the participant's core body temperature until it returns to baseline. Blankets can be applied to help with warming.

Remove the 3M SpotOn® zero-heat-flux forehead sensor and the Braun ThermoScan 7 tympanic sensor before escorting to MRI suite.

7.6.4 *VCool System Shut Down*

Turn the power switch on the VCool System to “OFF”

Turn off the flow meter

Remove the medical air hose from the flow meter

Disconnect the power cord

Wipe the exterior of the VCool System using the provided Caviwipes

Air delivery tube and cannula are disposable and should be discarded

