4 INVESTIGATIONAL PLAN

4.1 Study Design

This is a single-center, prospective, open label, feasibility study in healthy adult participants. Eligible participants who have signed an informed consent will be enrolled in the study. The participant will be assigned a unique ID number. After obtaining relevant demographic information, testing will ensue.

Baseline vital sign measurement (heart rate, temperature, blood pressure, respiratory rate) will be obtained. The participant will then undergo continuous MRI of the brain to include sequences that enable thermography. Baseline imaging sequences will take approximately 30 minutes. The investigator or designee will turn on the VCool System, while the VCool remains outside of the MRI suite, for up to two hours or until the target temperature of 35.5°C is reached. Body temperature will be continuously measured using a MRI compatible thermometer. During the cooling period and once endpoint is reached the participant will undergo repeated MRI with thermography. Once study endpoint is reached, the participant will be taken off of VCool and MRI thermography. If the target core body temperature is reached before 2 hours, the participant will be monitored until two hours are completed to determine if the VCool System can maintain the participant's core body temperature between 35°C and 36°C for one hour.

During the study, the participants will have their temperature monitored and will be assessed for shivering and adverse events.

Study participation is one visit lasting approximately 4 hours.

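### Sections 7.6.1 and 7.6.3 as written place a live cannula on the participant before the start reading and the recorded start of cooling, while Section 4.1 switches the device on only after baseline imaging, so time zero is not fixed

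*Protocol*

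**What the plan says.** All references are to the Protocol.

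- **Section 7.5** takes a baseline temperature with three sensors (forehead, tympanic, axillary) before the participant goes to the MRI suite and before any device step.
- **Section 7.6.1 (set-up)** switches on the power ("Turn the power switch to" ON), then says "Turn on gas and set flow meter to 35 liters per minute". It then checks the cold gas ("Confirm gas temperature setting at the end of the delivery tube is -5°C") and ends with "Attach nasal cannula to the delivery tube".
- **Section 7.6.3 (participant)** begins by having staff "place the nasal cannula on the participant, securing the straps around their head". Next come "Record the temperature from both temperature sensors and record the time" and a recording of the flow rate. Only after these does it say "Initiate the cooling and record the time", with induction allowed up to 2 hours.
- **Section 7.6.4 (shut-down)** holds the only instruction to turn off the flow meter.
- **Section 4.1** gives a different order: "Baseline imaging sequences will take approximately 30 minutes. The investigator or designee will turn on the VCool System", for up to two hours or until target.
- **Section 12.1** calculates the time and flow needed to reach 35.5°C from the measured baseline temperature, and the number of participants who get there in 2 hours or less.

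**The concern.** Once power, gas and flow are on and the cannula is fitted, the initiation step has no action of its own. Taken literally, exposure starts when the cannula goes on, and both the start reading and the recorded start time come afterwards. Section 4.1 has the device come on at a different point.

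The text therefore offers three candidate time zeros: device on, cannula on, and the initiation step. The first primary endpoint (35.5°C within 2 hours) and both calculations in Section 12.1 need exactly one. Section 2.2 also wants the data for cooling models based on flow rate and the time for which air is supplied, and that time is the quantity left uncertain.

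A late recorded start makes cooling look faster than it was. It can also lower the Section 7.6.3 start reading. If the baseline scan were affected, the reference for the brain-core comparison would shift too. The size of the lag would depend on the operator.

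**Working it through.** The plan gives no figure to reproduce. The check has two parts: the order of the steps, and an illustration of size.

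**1. Order of the steps**

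| Event | Sections 7.6.1 and 7.6.3 | Section 4.1 |
|---|---|---|
| Device and gas on | Set-up, before the cannula is fitted | After about 30 min of baseline imaging |
| Cannula on participant | First step of 7.6.3 | Not stated |
| Start temperature, time and flow | After the cannula is on | Baseline vital signs before imaging |
| Recorded start of cooling | After those recordings | Device turned on |
| Baseline MRI | Not placed relative to the cannula | Before the device is turned on |

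Two details support the reading that gas is already flowing at placement. The flow rate is recorded before the initiation step. And the overcooling instruction in 7.6.3 interrupts cooling by taking the cannula off and resumes it by putting the cannula back, with no gas step, so it treats cannula on as treatment on.

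**2. Size**

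Inputs: entry temperature 36.8 to 37.5°C (Section 6.1), target 35.5°C and limit 120 min (Section 5.1), baseline imaging about 30 min (Section 4.1). Assumptions: cooling is linear, and the participant needs exactly 120 min of exposure to reach target. The 2, 5 and 10 min lags are assumed, because the protocol gives no duration for these steps.

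- Fall required: 36.8 − 35.5 = 1.3°C; 37.5 − 35.5 = 2.0°C.
- Rate: 1.3 / 2 h = 0.65°C/h; 2.0 / 2 h = 1.0°C/h.
- Fall during the lag = rate × lag / 60. True exposure at a recorded 120 min = 120 + lag.

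| Lag | Fall at 0.65°C/h | Fall at 1.0°C/h | True exposure at recorded 120 min | Lag / 120 |
|---|---|---|---|---|
| 2 min | 0.022°C | 0.033°C | 122 min | 1.7% |
| 5 min | 0.054°C | 0.083°C | 125 min | 4.2% |
| 10 min | 0.108°C | 0.167°C | 130 min | 8.3% |
| 30 min | 0.325°C | 0.500°C | 150 min | 25.0% |

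The start reading lies between cannula placement and the initiation step, so its own shift is at most the fall shown for the full lag. For the 2-hour count, only a participant whose true time lies between 120 min and 120 min plus the lag changes category. With a lag of 2 to 5 min, that means a true time of up to 122 to 125 min. With 10 participants, one such case moves the proportion by 1/10, or 10 percentage points.

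**The case against.** The strongest reply is that the protocol shows its intent. It has a separate, timed initiation step after the start reading. Section 4.1 puts baseline imaging before the device is turned on, and Section 7.6.2 treats the controlled cooling period as a distinct phase. Nowhere does the text order early cooling; it leaves one step undefined. The instructions for use and the sponsor training mentioned in Section 17, which are not to hand, may say how the gas is held between set-up and initiation.

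The intent is clear, and that limits the point. It does not remove it, because the written steps do not deliver the intent: the gas is on, nothing stops it, and Sections 4.1 and 7.6.1 disagree on when the device comes on.

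A reader might infer two stronger claims that the documents do not support.

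- **That the study's baseline is contaminated.** The Section 7.5 temperatures precede every device step and cannot be affected. Only the Section 7.6.3 start reading is exposed under the literal order. The baseline scan is exposed only if a site fits the cannula with gas flowing before scanning, contrary to Section 4.1. Section 7.6.2 also sits between set-up and participant set-up, so section order alone would put imaging before placement.
- **That up to a quarter of the cooling goes unrecorded as a matter of course.** The 25% figure belongs to that same contrary-to-4.1 case. In the written sequence only two recordings separate placement from initiation, and the first is itself timed. The interval from that reading to initiation is therefore on record, and only the gap from placement to the reading is not.

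It is also fair to say that a few hundredths of a degree matters little when temperature is recorded every 2 minutes in a descriptive study of 10 participants.

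**Conclusion.** The point holds as a contradiction between stated steps that leaves time zero undefined. Read literally, Sections 7.6.1 and 7.6.3 start exposure before the start reading and before the recorded start time, and Section 4.1 says otherwise.

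The likely size is small: about 0.02 to 0.08°C and 2 to 5 minutes, resting on an assumed lag and linear cooling at 0.65 to 1.0°C/h. The larger case, about 30 minutes and 0.33 to 0.50°C, is conditional on the baseline scan being run under cooled air; it marks the outer limit of the ambiguity and is not an expected result. Participants who cool faster than these rates would lose more degrees per minute of lag, but their 2-hour classification would not be at risk.

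A second gap remains whatever the lag: Section 12.1 does not say whether its measured baseline temperature is the Section 7.5 or the Section 7.6.3 reading. The correction is worth making before enrolment, since untimed exposure cannot be recovered from the CRF afterwards.

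**What to change.** 1. Reconcile Sections 4.1, 7.6.1 and 7.6.3 into one order in which the start reading and the baseline MRI are completed before cooled air reaches the participant. Say where baseline imaging falls relative to cannula placement, and name the action that the initiation step stands for.
2. Add a CRF field for the time at which cooled air first reaches the participant. Use it as time zero for the time-to-target analysis and for the 2-hour count in Section 12.1.
3. State in Section 12.1 which reading is the measured baseline temperature.

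How long the device may be used is a clinical rule and is not proposed here. The passages on the 2-hour limit in Sections 4.1 and 7.6.3 need only be reconciled with this time zero.

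The cost is some reordering of existing text and one CRF field. A small downside is that the device may have to be pre-cooled with the participant not connected.

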3 STUDY DEVICE

3.1 Device Description

The VCool Intranasal Cooling System is intended to cool the core body temperature of patients for whom cooling is medically indicated. The VCool System produces a flow of thermoelectrically cooled air from an external source (hospital compressed wall medical air or oxygen). The air flow is delivered from the VCool System to the patient via an insulated air delivery tube. The air delivery tube is insulated to keep the air cooled. A two-prong nasal cannula is attached to the delivery tube and placed in the patient's nostrils. Cooled air enters the nasal passages and exits freely through the nose and mouth. The nasal prongs do not create a seal at the nostrils and therefore do not create excess airway pressure. The VCool System does not utilize invasive catheters, surface cooling pads, or any cooling agents. The VCool System is not used to deliver respiratory support.

The VCool is a small device weighing less than 25 pounds. There is an internal power source, a Peltier (thermoelectric cooling unit), air tubing, and thermistors. The system can deliver air flow rates of up to 40 liters per minute set to a temperature of 5°C at the end of the cannula. All parts of the system are constructed of biocompatible materials and designed for electrical safety. In this study, the VCool will be connected to a medical grade air compressor which will supply the air for cooling. A commercially available nasal cannula will be used to deliver the cooled air.

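### Does the -10°C check in section 7.6.1 contradict the set point of -19.0 entered a few steps earlier?

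*Protocol*

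**What the plan says.** The set-up list in section 7.6.1 of the protocol gives three temperature figures in this order.

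- In the controller program, before gas flows, the operator selects "Set Point and set value to -19.0". No unit is given.
- The operator then starts the air: "Turn on gas and set flow meter to 35 liters per minute".
- Next comes "Confirm temperature is set to -10°C". The component, display or sensor is not named.
- Then comes "Confirm gas temperature setting at the end of the delivery tube is -5°C". This step does name its point.
- Last comes "Attach nasal cannula to the delivery tube".

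Section 3.1 adds a fourth figure in describing what the device can deliver: air "set to a temperature of 5°C at the end of the cannula". It also lists the internal parts: "There is an internal power source, a Peltier (thermoelectric cooling unit), air tubing, and thermistors". Sensor locations are not given.

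During cooling, section 7.6.3 asks staff to "Record any VCool System adjustments to flow rate or temperature and record the new flow rate and temperature and time of adjustment". It does not say which of these temperatures is meant.

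**The concern.** The only value the operator has set before the first confirmation is -19.0. A step that then asks whether the temperature is set to -10°C looks like a check of that entry, and on that reading it fails. If it refers to some other point, the protocol does not say which. The omission stands out because the next step does give a location.

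At stake would be the consistency of the delivered intervention. Section 2.1 presents this as the first use of the method to lower core temperature. Section 2.2 wants cooling response modelled against air flow rate and time, which presumes that air temperature is the same across participants or reliably recorded. If operators read the step differently, the 10 participants could be cooled with air at different temperatures, or the temperature noted under section 7.6.3 could mean different things on different forms.

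**Working it through.** No sample size, power or error rate is involved, and the plan gives no derived figure to reproduce. The check compares the four figures and asks which reading fits the text.

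**Inputs**

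| Figure | Place | Unit | Measuring point | Step order |
|---|---|---|---|---|
| -19.0 | 7.6.1 | none | controller set point | before gas flow |
| -10 | 7.6.1 | °C | none | after gas is on |
| -5 | 7.6.1 | °C | end of delivery tube | after gas is on, before cannula is attached |
| 5 | 3.1 | °C | end of cannula | device description, not a set-up step |

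**Reading A: -10°C is the set point.**

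- If -19.0 is in °C, the gap is -10 - (-19.0) = 9°C.
- If -19.0 were in °F, it would be (-19.0 - 32) × 5/9 = -28.3°C, and the gap would be -10 - (-28.3) = 18.3°C. Nothing supports this unit. Every temperature in the protocol that carries a unit is in °C, including the next two set-up figures.

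In either unit the check fails, so Reading A makes the protocol contradict itself within a few lines.

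**Reading B: the figures are successive points along the air path, with -19.0 in °C.**

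- Controller to unnamed point: -10 - (-19) = 9°C rise.
- Unnamed point to tube end: -5 - (-10) = 5°C rise.
- Tube end to cannula end: 5 - (-5) = 10°C rise.

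The series rises steadily in the direction of flow, as cold air warming along a tube would. No check fails.

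**Which reading fits the text better?**

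1. *Order of steps.* Re-checking a typed set point needs no gas flow; checking air temperature does. Both confirmations follow the step that turns the gas on.
2. *Use of words.* The tube-end figure of -5°C is also called a setting, although it is plainly not the number entered in the controller. The protocol therefore uses this language loosely for gas temperatures, and the -10°C line need not repeat the set point.
3. *Hardware.* Section 3.1 lists more than one thermistor, so readings at more than one point are plausible.
4. *The 5°C figure.* It belongs to a statement of device capability and to a different point from the tube end. The 10°C difference is unexplained but is not a conflict.

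**Does it reach the analysis?** Section 12.1 calculates the time and flow rate needed to reach and hold the target, and counts participants who reach it within 2 hours. Delivered-air temperature is not an input. The rules in section 7.6.3 for holding the temperature range adjust flow only. The same set-up list applies to every participant.

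**The case for a change.** The strongest case for a change is that the protocol is the governing document. Section 18 forbids any use of the device other than as the protocol directs, and section 13.2 counts any failure to follow it as a deviation. A step with no stated measuring point cannot be shown from the text alone to have been met or missed. The benign reading has to be supplied by the reader. The language of setting is also a poor description of a downstream reading. Section 2.3.2 allows the device temperature to be adjusted, so the unlabelled temperature in section 7.6.3 could be recorded differently by two operators. Adding the labels would take only a few words.

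The wording point stands: -19.0 lacks a unit, the -10°C step lacks a location, and section 7.6.3 does not say which temperature is recorded. The consequence is not shown. That an operator would meet a mismatch or reset the device follows only under Reading A, which the text does not establish. Section 17 provides for sponsor training of all site staff on the device and procedures and refers to Instructions for Use. Those are not shown, but they are the usual place for sensor locations and displays. Section 7.6.3 already requires the new flow rate, temperature, time and reason to be recorded at each adjustment, and section 7.6.1 has controller data saved to a file for each participant, although its contents are not described.

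**Conclusion.** No change to the plan follows. The documents do not show that any of the four figures is wrong or that any two describe the same quantity. The 9°C gap is a contradiction only if the -10°C line restates the set point, and the order of steps and the wording of the next line point the other way. What remains is a clerical gap in device-operation detail that trained staff can be expected to fill.

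This rests on three assumptions: that -19.0 is in °C, that the three set-up figures refer to different points along the air path, and that training or device instructions identify those points. The first two are inferences from the text and the third cannot be checked here. If the sponsor knows that -10°C was meant as the set point, the two lines would have to be reconciled; the documents do not show which value would then be right. If the protocol is revised for other reasons, a unit, a location and a label for the temperature recorded in section 7.6.3 would tidy the text. The sample size and the primary analysis would be unaffected.

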2.3 Risk and Benefit Assessment

2.3.1 Potential Risks

The only known study-related risk is the use of a nasal cannula to deliver cold air to the participant. The potential risks associated with this delivery are:

Nosebleed

Shivering

Irritation of the nasal passages

Skin irritation at the site of the cannula

Nasal congestion

Over cooling

Participants will be de-identified using a study specific number at the time of enrollment. All Case Report Forms (CRFs) will be labeled with the de-identified participant identification (ID) number. No identifiable participant identification information will be provided to NeuroIntact.

Information collected for this study is confidential. However, officials of the Food and Drug Administration (FDA) or other regulatory agencies may research records during the ordinary course of carrying out their functions. A Sponsor representative may also inspect the research records to make certain the study data is accurate. The Investigator, regulatory agencies, and the Sponsor will protect the confidentiality of the records.

2.3.2 *Risk Mitigation*

The protocol has been designed to minimize the risks to study participants enrolled in the study. In general:

- Prior to study enrollment the Investigator must ensure the participant meets the inclusion/exclusion criteria
- Each participant will be fully informed about the conditions of study participation, and the risks and potential benefits of the study procedure and asked to provide an executed Informed Consent prior to being enrolled in the study
- Institutional Review Board (IRB) review and approval of the study protocol, Informed Consent Form, and any other participant-facing documents will be obtained prior to study initiation.
- The participant's core temperature will be continuously monitored with direction to adjust the VCool if the core temperature is $<35^{\circ}\text{C}$ for a sustained period of 5 minutes, to mitigate overcooling of the participant
- If the participant develops a nosebleed, the VCool will be stopped
- Participants will be assessed for shivering and if severe according to the Bedside Shivering Assessment Scale, the VCool flow and temperature will be adjusted

2.3.3 *Potential Benefits*

The information obtained in this study will not benefit the study participants directly but may aid future patients requiring cooling of body temperature.

2.4 *Study Rationale*

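### In the maintenance hour two rules for temperatures below 35°C give incompatible orders after 5 minutes, and the rule above 36°C can call for more flow than the device delivers

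*Protocol*

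**What the plan says.** **Below 35°C, general rule (Section 7.6.3).** The trigger is "If the core body temperature is <35°C for 5 minutes". The first action is "Remove nasal cannula, if temperature starts to rise after 2 minutes keep cannula off until temperature gets back to 35°C", after which the cannula is put back and treatment resumes. The second action is "If temperature continues to fall below 35°C after 2 minutes, cover patient with electric blanket that has been pre heated on standby". The rule comes straight after the statement that core temperature is monitored throughout the study. Nothing confines it to induction.

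**Below 35°C, maintenance rule (Section 7.6.3, later in the list).** "If temperature falls below 35°C., reduce flow rate by 5 liters per minute every 2 minutes until temperature rises back to 35°C". It has no 5-minute wait, no cannula removal and no blanket.

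**Below 35°C, risk summary (Section 2.3.2).** The device is to be adjusted if core temperature stays under 35°C "for a sustained period of 5 minutes, to mitigate overcooling of the participant". The kind of adjustment is not named.

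**Above 36°C (Section 7.6.3).** There is one rule: "increase flowrate 5 liters per minute every 2 minutes until temp falls below 36°C". It states no upper limit.

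**Device and settings.** Section 3.1 says "The system can deliver air flow rates of up to 40 liters per minute". Section 7.6.1 sets the starting flow at 35 L/min, and Section 7.6.3 permits 40 L/min after 10 minutes.

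**Analysis.** Section 12.1 will calculate the time and flow rate needed to reach and maintain the target temperature.

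**The concern.** Overcooling is a listed risk in Section 2.3.1, so the response to it should read the same way to everyone at the scanner. During the maintenance hour a participant below 35°C for more than 5 minutes falls under two rules. One says take the cannula off. The other says keep it on and go on reducing flow until 35°C is regained. Neither refers to the other.

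The data are affected too. Section 2.2 says the results will feed a control algorithm built on cooling response as a function of air flow, and Section 12.1 derives a maintenance flow rate. Minutes with the cannula off, or under an electric blanket, are not a response to any VCool flow. How many such minutes there are depends on which rule is followed. With 10 completers, different handling of one or two participants would show in the summary.

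On the warm side there is only one rule, but taken literally it can ask for a flow that the device cannot deliver.

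**Working it through.** The plan has no figure of its own to reproduce here. The check is step arithmetic on the protocol's settings.

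**Inputs**
- Starting flow F0: 35 L/min (7.6.1), or 40 L/min if raised after 10 minutes (7.6.3).
- Step: 5 L/min every 2 minutes (7.6.3).
- Device limit: 40 L/min (3.1).
- General rule: acts at 5 minutes below 35°C; delivered flow is then zero (7.6.3).
- Assumption: the protocol does not say whether the first cut is made at the first reading below 35°C (minute 0) or one interval later (minute 2). Both are shown.

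**Below 35°C**

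Flow after k cuts = F0 − 5k. By minute 5, cuts at minutes 0, 2 and 4 give k = 3; cuts at minutes 2 and 4 give k = 2. By minute 6, k = 4 or 3.

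| F0 (L/min) | First cut | Stepwise rule, 5 min | Stepwise rule, 6 min | Stepwise rule reaches zero | General rule after 5 min |
|---|---|---|---|---|---|
| 35 | minute 0 | 35 − 15 = 20 | 35 − 20 = 15 | minute 12 | 0 |
| 35 | minute 2 | 35 − 10 = 25 | 35 − 15 = 20 | minute 14 | 0 |
| 40 | minute 0 | 40 − 15 = 25 | 40 − 20 = 20 | minute 14 | 0 |
| 40 | minute 2 | 40 − 10 = 30 | 40 − 15 = 25 | minute 16 | 0 |

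At the 6-minute reading the two rules differ by 15 to 25 L/min of delivered flow. Before minute 5 there is no conflict in the orders, because the general rule is silent until then and the stepwise rule can be followed alone. The conflict starts at minute 5: the stepwise rule has its own end point (35°C regained), which has not been met, and the general rule removes the cannula.

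**Above 36°C**

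Steps available before the limit = (40 − F) / 5, where F is the flow when the rule starts.
- F = 35: (40 − 35) / 5 = 1 step. The second step asks for 45 L/min.
- F = 40: (40 − 40) / 5 = 0 steps. The first step asks for 45 L/min.
- If flow was lowered earlier, for example to F = 25: (40 − 25) / 5 = 3 steps, and only the fourth asks for 45 L/min.

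**What cannot be computed.** The protocol gives no cooling or rewarming rates, so the effect of either path on temperature, or on the length of an excursion, cannot be sized.

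**The case against.** The best reply is that the two rules below 35°C form an escalation: cut flow at once, and take the cannula off if 5 minutes pass without recovery. The different triggers make this plausible, and up to minute 5 it works. But the protocol does not say it, and the stepwise rule is written to run until 35°C is regained, not until minute 5. What stands is that the defect is a missing hand-over, which one sentence could supply.

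Other parts of the reply succeed and limit the point:
- Section 2.3.2 is a looser summary with the same 5-minute trigger as the general rule. A reader might count three contradictory responses, but the text supports two detailed rules and one vague summary.
- A reader might infer that low flows can never be tested in the maintenance hour. The documents do not support that. Two or three cuts fit before minute 5, and nothing resets the flow after recovery, so a later excursion could start from a lower setting.
- Above 36°C nothing contradicts another rule. The fault is a missing ceiling, and it matters only if flow starts at or near the limit or the excursion lasts long enough. Staff would presumably stop at 40 L/min, and a temperature above 36°C at full flow is itself a useful feasibility result.
- Section 7.6.3 already asks for each flow or temperature adjustment to be recorded with its time and reason, so much of the needed data will exist. That instruction does not name cannula removal or the electric blanket.

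**Conclusion.** The point holds as an inconsistency of instructions. From 5 minutes below 35°C in the maintenance hour, one rule leaves 20 to 25 L/min running from a start of 35 L/min (25 to 30 from 40) and the other leaves zero. The ranges rest on whether the first cut is immediate or 2 minutes later, and on flow standing at 35 or 40 L/min when the temperature falls. The rule above 36°C exceeds the device limit at the second step from 35 L/min or the first from 40, provided flow has not been reduced beforehand.

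The consequences are an ambiguous response to a listed risk, and a maintenance flow rate under Section 12.1 that depends on the rule staff choose.

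A reader might go further and infer that pass or fail of the maintenance endpoint (third in Section 5.1) turns on the choice of rule. That is not shown. The endpoint asks for 35 to 36°C for one hour. When the rules diverge, the participant has already been under 35°C for 5 minutes, so on a strict reading the endpoint has already failed. The same applies above 36°C. The protocol states no tolerance for excursions under which the result would change.

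**What to change.** - Reconcile Section 2.3.2, the general rule below 35°C and the maintenance rule in Section 7.6.3 into one written sequence, stating which instruction governs at each time in the maintenance hour. Which clinical rule applies is for the sponsor and investigator to decide.
- Make the rule above 36°C consistent with the 40 L/min limit in Section 3.1.
- When the maintenance flow rate in Section 12.1 is summarised, report time with the cannula off or the electric blanket on separately from time on VCool flow. Have the CRF capture start and stop times for both.

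The cost is a few lines of protocol wording and one or two CRF fields. Sample size, visit length and endpoints do not change.
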